5.8 Criteria for Removal from Study

Patients will be removed from study when any of the criteria listed in Section 5.5 applies. The reason for study removal and the date the patient was removed must be documented in the Case Report Form.

6. DOSE MODIFICATIONS

In young children less than 10 years of age where the study dose is not considered safe to deliver as a result of the radiation dose that will be delivered to surrounding normal tissues, a dose of 3500 cGy delivered in 700 cGy fractions in 5 fractions every day to the GTV, will be allowed as a prescription dose. A dose modification may be made at the discretion of the treating physician but the Principal Investigator must be informed and approve this change.

7. ADVERSE EVENTS: LIST AND REPORTING REQUIREMENTS

7.1 Adverse Events and Potential Risks

Because patients are receiving standard treatments, which are not part of this study, their treating physician will be counseling them on the risk of their treatments, including the risk of surgery, radiation therapy, and/or chemotherapy, whichever is appropriate for the type and the stage of their cancer. Clinically significant toxicities in the study will include Grade 3, 4, and 5 non hematologic toxicities. The procedures related to the study are phlebotomy, CT imaging, MRI imaging, and SBRT. Recording and reporting requirements are discussed in Section 7.3.

Risks associated with blood draw:

Phlebotomy can cause pain, bleeding, and rare needle site infection. CT imaging results in low dose radiation exposure, which has an extremely small risk of causing a secondary cancer.

Risks associated with SBRT:

It is difficult at this time to predict with confidence the complication rate from the proposed SBRT. However, it is reasonable to extrapolate from the current experience with SBRT to the spine, lung and pancreas in adults.

Toxicities commonly associated with such treatment will depend on the location of the treated metastasis. These toxicities can include skin erythema and desquamation, pain, neuropathy, dysphagia, nausea, vomiting, anorexia, and weight loss. Some of these symptoms can also be due to tumor progression. One significant toxicity is radiation pneumonitis, which can be manifested as fever, increased exertional dyspnea, pleuritic chest pain, and peritumoral infiltrate on chest imaging. It generally occurs between 1 to 3 months of completion of radiotherapy. The risk of grade 2-4 radiation pneumonitis is approximately 10-15% in patients treated with standard fractionated large field radiotherapy and higher in patients treated with combined chemoradiotherapy. It is highly dependent on the volume of the lung treated to high dose and the mean lung dose. At this point, the incidence of RT pneumonitis from stereotactic radiosurgery for small pulmonary tumors is unknown. However, if the treated tumor volume is kept \leq 65 cc, the risk should be $< 10-15\%$ with the proposed dose level. Also, given that this protocol focuses on SBRT to bone and spine, rather than lung, the risk of pneumonitis is expected to be low. Fracture is also a potential risk of radiotherapy to bone and spine, although doses in this study will be lower than the radiosurgery doses thought to put patients at high risk for fracture as reported in the literature (29).

Growth delay or arrest is a potential late effect of radiotherapy to bone for children who have not completed puberty. For this reason, patients in this protocol are limited

to those who have surgically unresectable disease or to those patients whose families refuse surgery. Given the data that demonstrates the improvement in clinical outcomes associated with aggressive local therapy in properly selected metastatic patients, the potential benefit of delivering a therapeutic dose of radiation likely outweighs the risks. The alternative treatment in this scenario is the delivery of subtherapeutic doses of radiation with palliative rather than curative intent.

Clinical and radiographic assessments will be performed as indicated to identify all adverse effects, ascertain their etiology, and provide the most appropriate palliative measures. Complications other than radiation pneumonitis, if any, will be graded according to the CTCAE version 4.0

7.2 Definitions

7.2.1 Adverse Event (AE)

An adverse event (AE) is any undesirable sign, symptom or medical condition or experience that develops or worsens in severity after starting the first dose of study treatment or any procedure specified in the protocol, even if the event is not considered to be related to the study.

Abnormal laboratory values or diagnostic test results constitute adverse events only if they induce clinical signs or symptoms or require treatment or further diagnostic tests.

7.2.2 Serious Adverse Event (SAE)

A serious adverse event (SAE) is any adverse event, occurring at any dose and regardless of causality that:

- Results in death
- Is life-threatening. Life-threatening means that the person was at immediate risk of death from the reaction as it occurred, i.e., it does not include a reaction which hypothetically might have caused death had it occurred in a more severe form.
- Requires or prolongs inpatient hospitalization (i.e., the event required at least a 24-hour hospitalization or prolonged a hospitalization beyond the expected length of stay). Hospitalization admissions and/or surgical operations scheduled to occur during the study period, but planned prior to study entry are not considered SAEs if the illness or disease existed before the person was enrolled in the trial, provided that it did not deteriorate in an unexpected manner during the trial (e.g., surgery performed earlier than planned).

- Results in persistent or significant disability/incapacity. Disability is defined as a substantial disruption of a person's ability to conduct normal life functions.
- Is a congenital anomaly or birth defect; or
- Is an important medical event when, based upon appropriate medical judgment, it may jeopardize the participant and require medical or surgical intervention to prevent one of the outcomes listed above. Examples of such medical events include allergic bronchospasm requiring intensive treatment in an emergency room or at home; blood dyscrasias or convulsions that do not result in inpatient hospitalization, or the development of drug dependency or drug abuse.

Events **not** considered to be serious adverse events are hospitalizations for:

- routine treatment or monitoring of the studied indication, not associated with any deterioration in condition, or for elective procedures
- elective or pre-planned treatment for a pre-existing condition that did not worsen
- emergency outpatient treatment for an event not fulfilling the serious criteria outlined above and not resulting in inpatient admission
- respite care

7.2.3 Expectedness

Adverse events can be 'Expected' or 'Unexpected.'

7.2.3.1 Expected adverse event

Expected adverse events are those that have been previously identified as resulting from administration of the agent. For the purposes of this study, an adverse event is considered expected when it appears in the current adverse event list, the Investigator's Brochure, the package insert or is included in the informed consent document as a potential risk.

Refer to Section 7.1 for a listing of expected adverse events associated with the study agent(s).

7.2.3.2 Unexpected adverse event

For the purposes of this study, an adverse event is considered unexpected when it varies in nature, intensity or frequency from information provided in the current adverse event list, the Investigator's Brochure, the package insert or when it is not included in the informed consent document as a potential risk.

7.2.4 Attribution

Attribution is the relationship between an adverse event or serious adverse event and the study treatment. Attribution will be assigned as follows:

- Definite – The AE is clearly related to the study treatment.
- Probable – The AE is likely related to the study treatment.
- Possible – The AE may be related to the study treatment.
- Unlikely - The AE is doubtfully related to the study treatment.
- Unrelated - The AE is clearly NOT related to the study treatment.

7.3 Recording and Reporting of Adverse Events

Participating investigators will assess the occurrence of AEs and SAEs at all participant evaluation time points during the study.

All AEs and SAEs whether reported by the participant, discovered during questioning, directly observed, or detected by physical examination, laboratory test or other means, will be recorded in the participant's medical record. Low grade toxicities are to be expected given the disease profile. Any toxicity below CTCAE v4.0 grade 3 will not be reported on the Master AE Log or Case Report Forms. However, this information will be monitored and retained in patient charts.

Hematologic toxicity will be assessed and monitored but not reported.

Hospitalization events occur within this patient population. Hospitalizations that occur greater than 30 days from completion of SBRT and that are not attributable to research intervention will be recorded on the Master AE Log and reported at the time of continuing review and SMC monitoring.

These parameters are drafted in accordance with CFR21, though provide realistic expectations based on the sickness of this patient population.

The descriptions and grading scales found in the revised NCI Common Terminology Criteria for Adverse Events (CTCAE) version 4.0 will be utilized for AE reporting. All appropriate treatment areas should have access to a copy of the CTCAE version 4.0. A copy of the CTCAE version 4.0 can be downloaded from the CTEP website at: http://ctep.cancer.gov/protocolDevelopment/electronic_applications/ctc.htm.

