1.2 Secondary Objectives

1.2.1 To describe the toxicity of SBRT delivered to a dose of 4000 cGy in 5 fractions of 800 cGy each for the population enrolled using grading with CTCAE v. 4.0

1.2.2 To assess clinical response rate of each treated site by serial CT assessment (FDG- PET/CT is optional for assessment)

1.2.3 To assess long-term clinical outcomes of this patient population after completion of SBRT by measuring relapse-free survival and overall survival

1.2.4 To assess quality of life following completion of SBRT using pre- and post-SBRT completion of the Brief Pain Inventory form and 10 point Visual Analog scale which will be filled out by the patient

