7.3.1.2 Participating Sites

Participating sites are responsible for reporting adverse events to their IRB according to its specific requirements and to the Coordinating Center as follows:

Fatal Events whether anticipated or unanticipated, and whether or not related to the study must be reported to the Coordinating Center within **24 hours** of the participating site Principal Investigator's learning of the event.

Serious and Unanticipated Adverse Events as defined above must be reported to the Coordinating Center within **24 hours** of the participating site Principal Investigator's learning of the event.

Other Serious Adverse Events which may result in a change to the protocol, informed consent, or risk to subjects as specified in the protocol must be reported within **three (3) working days** of the participating site Principal Investigator's learning of the event.

Adverse Events which result in no change to protocol, informed consent, or risk to subjects must be reported to the Coordinating Center on a monthly basis.

Adverse event reports are to be faxed or e-mailed to the Coordinating Center Study Coordinator. Follow-up reports are faxed, mailed, or sent electronically to the Coordinating Center as necessary.

The investigator must also report follow-up information about SAEs within the same time frames.

If a non-serious AE becomes serious, this and other relevant follow-up information must also be provided within the same time frames described above.

All SAEs must be collected whether or not they are considered causally related to the investigational product. Investigators and other site personnel are responsible for reporting all causally related SAEs to their IRB and the Protocol Chair.

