13.3 Analysis of Secondary Endpoints

13.3.1 Definition of secondary outcomes/endpoints:

- To describe the toxicity of SBRT delivered to a dose of 4000 cGy in 5 fractions of 800 cGy each for the population enrolled using grading with CTCAE v. 4.0
- The clinical response rate of each lesion will be assessed by serial CT assessment (FDG-PET/CT is optional for assessment) and defined by criteria as defined above. The absence of progression will constitute a response. Therefore, lesionspecific CR or SD will be measured as a response.
- To assess long-term clinical outcomes of this patient population after completion of SBRT by measuring relapse-free survival and overall survival. Relapse-free survival will be measured from time of enrollment to date of disease progression or death. Patients who are lost to follow-up will be censored for determination of

progression-free survival on the date of their last evaluation. Overall survival is defined as time from enrollment to death due to any cause.

- To assess quality of life following completion of SBRT using pre- and post-SBRT completion of the Brief Pain Inventory form and 10 point Visual Analog Scale which will be filled out by the patient at the treatment response intervals outlined above.

13.3.2 Analysis plan for secondary endpoints:

- Toxicities will be graded and tabulated at the time of each follow-up assessment. The proportion of toxicities by type and grade will be reported with exact 95% confidence intervals.
- Each metastatic lesion will be considered a target lesion and independently evaluated for response. The proportion of these lesions that have a stable or better response and the intra-cluster correlation will be estimated with an intercept only generalized estimating equation (GEE) regression. This will be estimated directly with SAS Genmod by specifying binomial variation, the identity link function, and an exchangeable correlation structure.
- Hazard rate estimates and 95% confidence intervals as well as Kaplan-Meier (KM) estimates will be used to summarize survival (OS), progression free survival (PFS), time to progression (TTP) and locoregional control (LRC) functions over time. The median OS, PFS, TTP and LRC will be reported. Cox proportional hazards models will be used to evaluate the impact of key covariates on these endpoints as the sample size permits.

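### Toxicity is to be reported by type and grade, but the case report forms will hold only grade 3–5 non-hematologic events

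*Combined protocol and SAP*

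**What the plan says.** All references are to the combined protocol and SAP.

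**What is to be reported.** Secondary objective 1.2.1 is to describe the toxicity of the regimen "for the population enrolled using grading with CTCAE v. 4.0". Section 13.3.2 sets out the analysis: "Toxicities will be graded and tabulated at the time of each follow-up assessment". It continues: "The proportion of toxicities by type and grade will be reported with exact 95% confidence intervals". Neither place limits this to severe events or leaves out hematologic ones.

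**What is to be collected.** Section 7.3 sets a floor: "Any toxicity below CTCAE v4.0 grade 3 will not be reported on the Master AE Log or Case Report Forms". On the low-grade events it says: "However, this information will be monitored and retained in patient charts". On blood toxicity it says: "Hematologic toxicity will be assessed and monitored but not reported". Section 7.1 gives the category of main interest: "Clinically significant toxicities in the study will include Grade 3, 4, and 5 non hematologic toxicities". Section 11.2 points to that definition for the safety rule.

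**What sites send.** Section 7.3.1.2 sets a monthly cycle for the remaining events (the quote stops one word short of the end of the sentence): "Adverse Events which result in no change to protocol, informed consent, or risk to subjects must be reported to the Coordinating Center on a monthly". It names no grade. The data schedule in section 10.1 lists an Adverse Event Report Form due after each visit. The study calendar in section 8 has a toxicity assessment during SBRT and at every follow-up visit, and a blood count at every follow-up visit.

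**The concern.** The analysis section describes a table covering every type and grade of toxicity. The collection section keeps part of the data for that table off the forms that would feed it. A statistician who followed both sections exactly could not fill in the lower grades.

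The gap falls where events are most likely. Section 7.3 itself expects low-grade toxicity. Several effects that section 7.1 lists as common, such as skin reddening, nausea, loss of appetite and pain, can occur at low grade. The protocol summary says that SBRT has been little studied in children, and section 7.1 concedes that complication rates for this use are hard to forecast. A description of tolerability is therefore one of the useful products of a 20-patient single-arm trial. At stake is whether the report delivers the toxicity description that the objective promises or a narrower one.

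**Working it through.** The plan gives no figure to reproduce on this point. The check compares what is promised with what is captured.

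**Step 1. Cells of the planned table.** Inputs: 1.2.1 and 13.3.2 for the promise; 7.1 and 7.3 for the capture.

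| Toxicity | Promised in 13.3.2 | On the forms under 7.3 | Proportion obtainable from the forms |
|---|---|---|---|
| Non-hematologic, grade 3, 4, 5 | Yes | Yes | Yes |
| Non-hematologic, grade 1, 2 | Yes | No (explicit) | No |
| Non-hematologic, any grade | Yes, by summing grades | Grade 3–5 part only | No |
| Hematologic, all grades | Yes (no exclusion stated) | No, by inference for grade 3–5 | No, if the inference is right |

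The last row needs care. The sentence that names the case report forms concerns events below grade 3. The hematologic sentence says only that such toxicity is not reported. Reading it as also off the forms is reasonable, but it is a reading.

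**Step 2. Other routes for the missing data.** Charts keep the low-grade events, but no section plans to abstract them. The monthly rule in 7.3.1.2, read literally, would send low-grade events to the Coordinating Center, while 7.3 keeps them off the log and the forms. A site cannot tell from the text what to do with a grade 2 event. The list of required report contents in 7.3.1.1 does not include the grade.

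**Step 3. What the forms can say about any-grade toxicity.** Take n = 20 treated patients (section 13.2) and read a proportion as patients affected out of patients treated. If x patients have a given toxicity at grade 3–5, the other 20 − x may or may not have had it at grade 1–2. The any-grade sample proportion then lies between x/20 and (x + (20 − x))/20 = 100%.

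- x = 0: between 0% and 100%.
- x = 2: between 2/20 = 10% and 100%.

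An absent entry therefore cannot be read as no low-grade event.

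**Step 4. Exact intervals for the cells that are available.** The Clopper–Pearson 95% limits are the 2.5% quantile of Beta(x, n − x + 1) and the 97.5% quantile of Beta(x + 1, n − x). For x = 0 the upper limit is 1 − 0.025^(1/20) = 0.168.

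| x of 20 | Exact 95% interval |
|---|---|
| 0 | 0 to 16.8% |
| 2 | 1.2 to 31.7% |
| 5 | 8.7 to 49.1% |
| 10 | 27.2 to 72.8% |

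These can be produced for grade 3–5 non-hematologic toxicity, and they would be the same if every low-grade event were also collected. The defect is a set of missing cells, not a loss of precision in the cells that remain.

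**Step 5. Reach.** The primary endpoint is local control at 6 months and uses no toxicity data. The section 11.2 rule takes its criteria from 7.1, which are grade 3–5 non-hematologic events, and those are not barred from the forms.

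**The case against.** The floor is deliberate and defensible. Section 7.3 gives its reason: low-grade effects are expected in this population. Section 7.1 notes that some of the listed symptoms may come from tumor progression, and chemotherapy is allowed from two weeks after SBRT (section 3.2.4). In a single-arm trial, mild nausea, poor appetite or low counts would be hard to attribute. The events that the protocol calls clinically significant are captured, and the low-grade ones remain in the charts of only 20 patients, where they could be retrieved.

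Much of this stands. A reader might infer that the toxicity objective cannot be answered from the trial data at all. The documents do not support that: grade 3, 4 and 5 non-hematologic toxicity can be tabulated by type with exact intervals, so the objective is answerable in part.

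The objection does not remove the mismatch. The floor appears in 7.3 but not in 1.2.1 or 13.3, where the reported quantity is defined. Keeping events in charts is not a plan to collect them. Section 7.3.1.2 does not fill the gap either, because it contradicts 7.3 instead of qualifying it.

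**Conclusion.** The point holds as an inconsistency between the stated toxicity analysis and the stated data capture. The forms support grade 3–5 non-hematologic proportions. They do not support grade 1, grade 2 or any-grade proportions and, if not reported means off the forms, they do not support hematologic ones. The monthly rule in 7.3.1.2 is a second, unreconciled conflict with 7.3.

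Three further inferences should be resisted:

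- **That all hematologic toxicity is expressly barred from the case report forms.** The text does not say so; this is a fair reading only.
- **That the 0 to 16.8% interval for 0 of 20 measures the damage.** It would not change with full low-grade capture.
- **That readers would take empty cells as absence of toxicity.** The documents give no basis for this, and a report can state its grade floor.

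The conclusion rests on the current text of 1.2.1, 7.3 and 13.3, and on there being no chart abstraction plan elsewhere in the documents. It does not depend on the number of patients or on any assumed toxicity rate. It is worth correcting because the reported endpoint should match the data, but it leaves the primary endpoint and the safety stopping rule untouched.

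**What to change.** Choose one of two changes.

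**(a) Widen the capture.** Amend 7.3 so that, at each visit, the highest CTCAE grade of each toxicity type is entered with its attribution on the Adverse Event Report Form already listed in 10.1, for all grades. State whether hematologic toxicity is included; if it is not, say so in 1.2.1 and 13.3 as well. Attribution should be recorded, not used as a filter, because 13.3.2 is not restricted to treatment-related events. The cost is modest extra data entry. The calendar has one assessment period during SBRT and nine follow-up visits, so at most 20 × (1 + 9) = 200 patient-assessments, all of which are already scheduled. The drawback is that some low-grade events will be hard to attribute without a control group.

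**(b) Narrow the claim.** Restate 1.2.1, 13.3.1 and 13.3.2 as grade 3–5 non-hematologic toxicity. This costs only a wording change. The drawback is a narrower toxicity description.

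Under either option, reconcile 7.3 with 7.3.1.2 so that sites know which grades go on the log and forms and which go in the monthly report, and add grade to the report contents listed in 7.3.1.1.

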7.3.1 Reporting Requirements

7.3.1.1 Adverse Events Reports

The Coordinating Center is the central location for the collection and maintenance of documentation of adverse events and is responsible for submitting adverse event reports to the Protocol Chair promptly. The Coordinating Center will maintain documentation of all adverse event reports for each participating site. Adverse event reports submitted to the Coordinating Center must be signed and dated by the participating site's Principal Investigator. The Coordinating Center will provide appropriate forms to be used by all participating sites for reporting adverse events. Information to be provided must include:

- Subject ID number, and initials
- Date of the event
- Description of the event
- Description of site's response to the event
- Assessment of the subject's condition
- Subject's status on the study (on study, off study, etc.)
- Attribution of event to study treatment

